Antiplatelet Effects of Evolocumab in Patients with Peripheral Arterial Disease

Principal Investigator: [name].

Co-Investigators: [name].

Drug Name: Evolocumab

Sponsor: Inova Heart and Vascular Institute at Inova Fairfax Hospital,
Falls Church, VA

Site of Investigation: Inova Heart and Vascular Institute at Inova Fairfax Hospital,
Falls Church, VA

Protocol Version Date: 19-December-2018

Contact Information:

[name].

Inova Center for Thrombosis Research and Drug Development,

Inova Heart and Vascular Institute

[name]

[name]

[contact],

[contact]

Email: [contact]

PROTOCOL SYNOPSIS

Title: Antiplatelet Effects of Evolocumab in Patients with Peripheral Arterial Disease

Short Title: Antiplatelet effects of Evolocumab

Rationale: Peripheral arterial disease (PAD) affects about 8.5 million Americans aged ≥ 40 years. PAD is the third leading cause of atherosclerotic vascular morbidity after coronary heart disease and stroke.^{1,2} Statin therapy has been shown to improve walking performance, resting and post-exercise ABI and claudication.³ In addition, higher statin doses and lower LDL-cholesterol levels have been shown to be independently associated with improved outcomes in PAD patients.⁴ The latter finding indicates that significantly lower LDL-cholesterol may be associated with better clinical outcomes and supports proprotein convertase subtilisin/kexin type 9 (PCSK9) antibody therapy in patients with PAD. A relation between dyslipidemia, oxLDL levels, high plasma fibrinogen levels and platelet activation has been demonstrated in patients with CVD.⁵⁻⁷ In addition to LDL cholesterol reduction and plaque stabilization, other mechanisms of PCSK9 antibodies may further mitigate cardiovascular risk in patients with PAD.

Objectives

Primary: To study the effect of evolocumab + high dose statins on platelet activation and platelet aggregation.

Secondary: To study the effect of evolocumab + high dose statins on lipid profile, oxLDL, soluble LOX-1 receptor, fibrinogen, hsCRP, p-selectin, atherox (Soluble markers), Urinary 11-dh-TxB2 and 8-iso-prostaglandin F2 α levels.

Exploratory: To study the effect of evolocumab + high dose statins on platelet-fibrin clot characteristics and shear-induced platelet aggregation.

Study Type: Single arm-open label study design.

Study Design: This is a phase IV, prospective pharmacodynamic study.

Study Methodology: This investigation will be conducted in subjects >18 years of age with PAD. Platelet activation and aggregation, and biomarkers associated with platelet activation, oxidative stress, and inflammation will be assessed at the screening (baseline), after 8 weeks of high-dose statins and 24 hours and 8 weeks after high dose statin + evolocumab therapy (study flow diagram).

Patients: Sixty patients with a history of Peripheral Artery Disease (PAD) including carotid artery disease.

Statistical Methodology: Categorical variables will be compared using χ^2 test or the Fisher exact test whereas continuous variables will be assessed using either paired test or Wilcoxon signed rank test after checking for normal distribution. Analyses will be performed with SPSS software (SPSS, Inc., Chicago, IL) and $p < 0.05$ will be considered significant

INTRODUCTION

1.1 Specific Aims

To measure platelet activation and aggregation, soluble biomarkers, clot characteristics and shear-induced platelet aggregation at the baseline, after 8 weeks of high-dose statins and 24 hr and 8 weeks after high-dose statins + evolocumab therapy (study flow diagram).

- **Platelet Aggregation:**
Adenosine diphosphate (ADP)-, Arachidonic acid (AA)-, and collagen-induced platelet aggregation by light transmittance aggregometry.
- **Platelet activation markers:**
P-selectin, CD36, LOX-1, basigin (CD147, receptor for glycoprotein VI), oxLDL on platelets by flow cytometry.
- **Lipid profile and soluble markers:**
Lipid profile including LDL-C measurement by conventional laboratory methods and soluble markers such as oxLDL, LOX-1 receptor, fibrinogen, hsCRP, p-selectin, Atherox in plasma by enzyme linked immunoassay.
- **Platelet-fibrin clot characteristics:**
Thrombin-induced platelet-fibrin-clot strength, time to initial thrombin generation, and functional fibrinogen by thrombelastography (TEG6S).
- **Shear-induced platelet aggregation:**
Shear-induced platelet aggregation by T-TAS perfusion flow chamber analysis.
- **Urine 11-dh-TxB2 and 8-iso-prostaglandin F2 α**
Urinary 11- dehydrothromboxane B2 level using The AspirinWorks™ ELISA (Corgenix) and urinary 8-iso-prostaglandin F2 α analysis using Cayman's 8-Isoprotane ELISA kit.

To measure ankle-brachial index (ABI) at baseline, after 8 weeks of high dose statin therapy (Visit 2), and 8 weeks after high-dose statins + evolocumab therapy (Visit 5) to determine the severity of peripheral arterial disease (PAD) and response to evolocumab treatment on endothelial function.

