1.3 Background and Significance

Peripheral arterial disease affects about 8.5 million Americans aged ≥ 40 years. PAD is the third leading cause of atherosclerotic vascular morbidity after coronary heart disease and stroke.^{1,2} PAD is a manifestation of diffuse systemic atherosclerosis that coexists with coronary artery and cerebroarterial disease. Patients with PAD often have a very large atherosclerotic burden and large atherosclerotic burden has been associated with heightened platelet reactivity measured in systemic circulation.⁸ About 10–20% of people with PAD have intermittent claudication, another 50% have atypical leg symptoms, and those without exertional leg pain have poor mobility compared with individuals without peripheral symptoms. Patients with PAD have roughly a three-fold increase in risk of mortality compared with those without peripheral artery disease.² Ankle-brachial index (ABI) measurement is a well-established tool, to identify PAD.

With the expanding size of the elderly population, PAD is similarly a major growing clinical problem with limited current therapeutic options. Patients with PAD primarily die from thrombotic events - heart attack and stroke. The current antithrombotic agents administered for prophylaxis are aspirin and clopidogrel.⁹ High LDL is a major risk factor for PAD and therefore lipid-lowering therapy constitutes another important therapeutic intervention for patients with PAD. Statin therapy has been shown to improve walking performance, resting and post-exercise ABI and claudication.³ In addition, higher statin doses and lower LDL-cholesterol levels have been shown to be independently associated with improved outcomes in PAD patients.⁴ The latter finding indicates that significantly lower LDL-cholesterol may be associated with better clinical outcomes and supports proprotein convertase subtilisin/kexin type 9 (PCSK9) antibody therapy in patients with PAD.

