2.1.1 Eligibility criteria

- Inclusion criteria
 - History of Peripheral Artery Disease (PAD).
Defined as one or more of the following:
 - Documented history of PAD
 - Previous limb or foot amputation for arterial vascular disease (i.e., excludes trauma),
 - Carotid artery disease (defined as >50% stenosis or prior revascularization)
 - Subject may be of either sex and of any race, and must be >18 years of age
 - Subject agrees to not participate in any other investigational or invasive clinical study for a period of 4 months during the study period
 - Subject must be willing and able to give appropriate informed consent
 - The subject is able to read and has signed and dated the informed consent document including authorization permitting release of personal health information approved by the investigator's Institutional Review Board (IRB)
 - Subjects who are either statin-naïve or already on statin and are willing to be started on high dose (HD) statin therapy:
 - If not on statin→start HD statin therapy (atorvastatin 40mg or rosuvastatin 20mg as according to investigator discretion)
 - If on atorvastatin 40 mg once a day→continue
 - If on lovastatin, pitavastatin, simvastatin, or pravastatin→change to atorvastatin 40 mg once a day
 - If on atorvastatin 80mg once a day→continue
 - If on rosuvastatin 20 to 40mg once a day→continue
 - If on rosuvastatin 10mg once a day→increase to 20mg once a day
- **Exclusion criteria:** Subjects will be excluded from entry if ANY of the criteria listed below are met:
 - Prior use of any PCSK9 inhibition treatment
 - Participation in any investigational study within the last 60 days.
 - Severe renal dysfunction, defined as an eGFR <20 mL/min/1.73 m², or creatinine kinase (CK) level at 10 X ULN at screening.
 - Active liver disease or hepatic dysfunction, defined as AST or ALT >3 x ULN as determined by central laboratory analysis at screening
 - Recipient of any major organ transplant (e.g., lung, liver, heart, bone marrow, renal)
 - Known major active infection or major hematologic, renal, metabolic, gastrointestinal, or endocrine dysfunction in the judgment of the investigator

- Malignancy (except non-melanoma skin cancers, cervical in situ carcinoma, breast ductal carcinoma in situ, or stage 1 prostate carcinoma) within the last 5 years

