Relative difference = 100 * (baseline on high dose statin value – post high dose statin plus evolocumab value) / baseline on high dose statin value

3.1.1 **Secondary Endpoints**

- Relative differences in AA- and collagen-induced platelet aggregation between high dose statin therapy and evolocumab plus high-dose statin therapy.

- Relative differences in platelet bound p-selectin, oxLDL, soluble LOX-1 receptor, between high dose statin therapy and evolocumab plus high-dose statin therapy.
- Relative differences in lipid profile, oxLDL, soluble LOX-1 receptor, fibrinogen, hsCRP, p-selectin, atherox (soluble markers) between high dose statin therapy and evolocumab plus high-dose statin therapy.
- Relative differences in platelet-fibrin clot characteristics and shear-induced platelet aggregation between high dose statin therapy and evolocumab and high-dose statin therapy
- Relative differences in ABI between high dose statin therapy. and evolocumab and high-dose statin therapy
- Relative differences in urinary 11-dh-thromboxane B2 levels between high dose statin therapy and evolocumab plus high-dose statin therapy.
- Relative differences in urinary 8-iso-Prostaglandin F2 α levels between high dose statin therapy and evolocumab plus high-dose statin therapy.

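### The ABI aim claims an evolocumab response on endothelial function that no planned test measures, and the ABI endpoint has no analysis set or limb rule

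*Combined protocol and SAP*

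**What the plan says.** - **Aim.** Section 1.1 (Specific Aims) gives ABI two purposes: "to determine the severity of peripheral arterial disease (PAD) and response to evolocumab treatment on endothelial function". The last measurement is "8 weeks after high-dose statins + evolocumab therapy (Visit 5"; Table 1 places it 8 weeks after the first evolocumab dose.
- **What ABI is said to show.** Section 1.3 states: "Ankle-brachial index (ABI) measurement is a well-established tool, to identify PAD". It also states: "Statin therapy has been shown to improve walking performance, resting and post-exercise ABI and claudication". Neither sentence concerns the endothelium.
- **Who enters.** Section 2.1.1 lists the PAD criteria under "Defined as one or more of the following". One is "Carotid artery disease (defined as >50% stenosis or prior revascularization"; another is "Previous limb or foot amputation for arterial vascular disease". No ABI threshold or evidence of leg disease is required.
- **Endpoint.** Section 3.1.1 lists "Relative differences in ABI between high dose statin therapy" and combined therapy among seven secondary endpoint bullets, with no analysis population and no endothelial wording.
- **Method.** Section 2.2 describes the blood and urine assays but has no ABI procedure. Table 1 schedules ABI at Visits 1, 2 and 5.

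**The concern.** There are two separate problems.

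The first is a claim without a measurement. ABI is a ratio of ankle to arm pressure. A change in it is evidence about limb arterial disease. The plan gives no reason to read it as evidence about the endothelium, so a reported endothelial response would rest on nothing the trial measured.

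The second is an endpoint that is not fully defined. A patient who qualified on carotid disease and has healthy legs has an ABI, but it does not grade the qualifying disease and has little room to improve. A patient who qualified by amputation may have no ankle pressure on that side. The plan does not say whether such patients contribute, which leg is used, or whether it is the same leg at every visit. In an open-label, single-arm study those choices could be made after the data are seen, and a pooled null result would say little about diseased legs.

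**Working it through.** **Step 1. Is there any endothelial measure?** Sections 1.1, 2.2 and 3.1.1 and Table 1 list aggregation, platelet flow cytometry, lipids and soluble markers, clot characteristics, shear-induced aggregation, two urinary markers and ABI. None is described as a test of endothelial function. Section 1.3 ties ABI to identifying PAD and to statin response. The endothelial clause in Section 1.1 therefore has no support elsewhere in the document.

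**Step 2. What can still be answered?** Severity of leg disease at each visit and within-patient change from Visit 2 to Visit 5 need only a measurable ankle pressure. A carotid-only patient has one, and an amputee may have one in the other leg.

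**Step 3. Is the plan's own sample size relevant?** Section 3.2 gives a difference of 14, SD 30, n = 50, two-sided alpha 0.05, 91% power and 16% dropout.
- Standardized effect: 14/30 = 0.467.
- Normal approximation: Φ(0.467 × √50 − 1.96) = Φ(1.34) = 0.910. The exact paired t-test gives 0.899.
- Total: 50/(1 − 0.16) = 59.5, so 60.

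The figure reproduces, but it is for ADP-induced aggregation only. No ABI effect, ABI SD or ABI power is stated.

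**Step 4. Dilution.** Let f be the share of contributing patients without leg disease. Then

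pooled mean change = (1 − f) × change with leg disease + f × change without.

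If the second change is zero, this is (1 − f) × the leg-disease change. The same factor applies to a mean of per-patient relative differences.

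**Step 5. Illustration only.** Assumptions, none from the document: the values of f; 50 completers; zero change in patients without leg disease; the same SD in everyone; and a standardized effect of 0.467 in leg-disease patients, borrowed from the aggregation calculation because there is no ABI figure. Power is by exact paired t-test. The last column is the standardized change detectable at 80% power once the others are left out.

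| f | Share of change left if pooled | Power, all 50 pooled | n if left out | Power if left out | Detectable at 80% |
|---|---|---|---|---|---|
| 0 | 100% | 0.899 | 50 | 0.899 | 0.404 |
| 10% | 90% | 0.829 | 45 | 0.865 | 0.427 |
| 20% | 80% | 0.735 | 40 | 0.821 | 0.454 |
| 30% | 70% | 0.620 | 35 | 0.765 | 0.487 |
| 50% | 50% | 0.366 | 25 | 0.610 | 0.584 |

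Under these assumptions, leaving out patients who cannot change loses less power than pooling them. The table shows direction, not an estimate for this trial.

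**The case against.** The strongest case on the other side has four parts.

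1. **ABI does have a documented role as a response measure.** Section 1.3 cites a statin effect on resting and post-exercise ABI, which is a stated reason to follow it under further lipid lowering. This stands. It supports change in ABI as an endpoint, but not the endothelial reading.
2. **The plan does not instruct pooling or an endothelial report.** A reader might infer that every ABI change will be pooled over all patients and reported as an endothelial effect. The document does not say so. Section 3.1.1 names no analysis population and has no endothelial wording, and the hypothesis in Section 1.2 mentions neither ABI nor the endothelium. The defect is silence on the analysis set and an unsupported clause in the aim.
3. **Carotid entry does not mean healthy legs.** Section 1.3 describes PAD as part of diffuse atherosclerosis that coexists with disease in other beds. Some carotid-qualified patients will therefore have leg disease, so f is at most the carotid-only share and may be well below it. This stands.
4. **The stakes are low.** ABI is absent from the synopsis objectives, is one of many secondary measures and is unpowered. Including carotid disease is a declared choice in a platelet study. This stands, and it sets the severity.

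**Conclusion.** The endothelial part of the ABI aim cannot be answered with the planned data, whatever the result. That follows from the text alone and needs no assumption.

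A reader might go further and infer that the whole ABI aim is unanswerable because of who is enrolled. The document does not support that. Severity of leg disease and the Visit 2 to Visit 5 change remain measurable in patients with a usable ankle.

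Dilution by patients without leg disease is possible, but its size is unknown. The factor of one minus their share holds only if they are pooled and show no change, and the plan gives neither the share nor an expected ABI effect. Separately, with no concurrent control, even a well-defined ABI change cannot be separated from time or from continued statin treatment.

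This is a minor item that does not touch the primary endpoint.

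**What to change.** 1. In Section 1.1, delete the reference to endothelial function and state the aim as change in ABI, a measure of limb arterial disease. Add that in a single-arm study this change cannot be separated from time or continued statin effect.
2. Pre-specify the main ABI analysis as the Visit 2 to Visit 5 change in patients with lower-limb PAD and a measurable ankle pressure. Patients with both carotid and leg disease belong in this set. Use the same index limb at every visit: the intact leg with the lower Visit 1 ABI. Fixing the limb at Visit 1 reduces regression to the mean in the later contrast; it removes it only if Visit 1 error is independent of error at Visits 2 and 5.
3. Report all other patients who have an ABI, including carotid-only patients, descriptively. Give the all-patient result as a supporting analysis.
4. Add a short ABI method to Section 2.2 that records each leg separately and says how an amputated or unmeasurable limb is handled.

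The cost is wording and an analysis-set definition, with no new visit or assay. The limb rule does need ABI recorded by leg and leg disease noted at Visit 1, which the plan does not state. The downside is a smaller n in one unpowered secondary endpoint: 45 down to 25 of 50 completers if 10% to 50% fall outside the set (assumed).

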1.2 Hypothesis

Treatment with evolocumab plus high-dose statin is associated with a reduction in platelet activation and aggregation and biomarkers associated with platelet activation, oxidative stress, and inflammation.

1.3 Background and Significance

Peripheral arterial disease affects about 8.5 million Americans aged ≥ 40 years. PAD is the third leading cause of atherosclerotic vascular morbidity after coronary heart disease and stroke.^{1,2} PAD is a manifestation of diffuse systemic atherosclerosis that coexists with coronary artery and cerebroarterial disease. Patients with PAD often have a very large atherosclerotic burden and large atherosclerotic burden has been associated with heightened platelet reactivity measured in systemic circulation.⁸ About 10–20% of people with PAD have intermittent claudication, another 50% have atypical leg symptoms, and those without exertional leg pain have poor mobility compared with individuals without peripheral symptoms. Patients with PAD have roughly a three-fold increase in risk of mortality compared with those without peripheral artery disease.² Ankle-brachial index (ABI) measurement is a well-established tool, to identify PAD.

With the expanding size of the elderly population, PAD is similarly a major growing clinical problem with limited current therapeutic options. Patients with PAD primarily die from thrombotic events - heart attack and stroke. The current antithrombotic agents administered for prophylaxis are aspirin and clopidogrel.⁹ High LDL is a major risk factor for PAD and therefore lipid-lowering therapy constitutes another important therapeutic intervention for patients with PAD. Statin therapy has been shown to improve walking performance, resting and post-exercise ABI and claudication.³ In addition, higher statin doses and lower LDL-cholesterol levels have been shown to be independently associated with improved outcomes in PAD patients.⁴ The latter finding indicates that significantly lower LDL-cholesterol may be associated with better clinical outcomes and supports proprotein convertase subtilisin/kexin type 9 (PCSK9) antibody therapy in patients with PAD.

Monoclonal antibodies against PCSK9 are innovative agents that provide very potent LDL reduction when administered on top of statins. PCSK9 antibodies prevent LDL receptor degradation and enhance circulatory LDL cholesterol clearance. The lower LDL cholesterol levels potentially enhance the stabilization of vulnerable plaque in both culprit and non-culprit vessels following the index event.¹⁰ Increased PCSK9 levels have been correlated with cardiovascular event occurrence.^{11,12} Elevated LDL levels result in the generation of proinflammatory oxidized (ox) LDL and augmentation of plaque vulnerability. Levels of circulating lectin-like oxLDL receptor-1 (LOX-1), a major ox-LDL receptor, are elevated in patients with ACS, with a diagnostic sensitivity and specificity superior to high-sensitivity C-reactive protein to identify patients with ACS. LOX-1 receptor expression is inducible by proinflammatory stimuli in a dynamic fashion.^{13,14} LOX-1 receptor activation induces oxLDL uptake, increased production of cell-surface adhesion molecules and a state of oxidative stress and inflammation- key steps involved in the progression of atherosclerosis and destabilization of plaque. Recent studies indicate a cross-reactive mechanism of PCSK9 and LOX-1 that leads to a mutually amplified proinflammatory response.¹⁵

In addition, a relation between dyslipidemia, oxLDL levels, high plasma fibrinogen levels and platelet activation has been demonstrated in patients with CVD.⁵⁻⁷ OxLDL activates platelets and promotes adhesion to dysfunctional endothelium.^{16,17} A proposed mechanism of oxLDL-induced platelet activation includes binding of oxLDL to the ApoB/E receptor (APOB/E-R) and platelet endothelial adhesion molecule (PECAM-1) leading to the generation of TxA₂ mediated by p38MAPK and cytosolic phospholipase A₂ (cPLA₂). The latter platelet activation is synergistic with platelet responses to other agonists such as

adenosine diphosphate, collagen, and thrombin leading to platelet aggregation. The interaction between oxLDL and scavenger receptor A (SRA) and CD36 are also known to activate platelets via cPLA2 and p38MAPK-mediated mechanisms. A recent animal study suggested that platelet activation associated with oxLDL and hyperlipidemia is due to generation of reactive oxygen species (ROS) through a CD36-protein kinase C (PKC) pathway and modulation of cGMP signaling.¹⁸ Finally, plasma PCSK9 levels were also positively and independently correlated with increased platelet count and plateletcrit.¹⁹

The mainstay therapy of patients with PAD is aspirin and statin therapy. Chaudhary et al. demonstrated that patients with atherosclerosis on aspirin and lipid lowering therapy was associated with significantly lower levels of inflammation and thrombogenicity as measured by urinary 11-dTxB2.²⁰ Secondly, another urinary measure which has shown to be a marker of inflammation /oxidative stress is Urinary 8-iso-PGF2 α . There is no information on the relationship of PCSK9 therapy on urinary 11-dTxB2 and 8-iso-PGF2 α levels.²¹

